5.4 Correlative Studies

The presence of the E-selectin ligand on AML blasts in the bone marrow will be assessed using flow cytometry. Gene expression profiling via RNA analysis will be performed to include the quantification of gene products responsible for E-selectin ligand expression. Levels of soluble E-selectin will be assessed using ELISA. Samples will be obtained as detailed in the Correlative Study Collection Table and sent to a central laboratory for testing. Any missed collection of samples for correlative studies during the Pre-Treatment evaluation and/or during Treatment evaluation will not be considered a protocol deviation.

Correlative Study Collection Table 3

Procedures	Pre Treatment	Cycle 1											
	≤ 14 d prior to Day 1	Day 1	Day 2	Day 3	Day 4	Day 5	Day 6	Day 7	Day 8	Day 9	Day 10	Day 11	Day 12
Cladribine Administration ^A		X	X	X	X	X							
Cytarabine Administration ^A		X	X	X	X	X	X	X	X	X	X		
Uproleselan Administration ^B		X	X	X	X	X	X	X	X	X	X	X	X
Bone Marrow Aspirate Collection (E-selectin Ligand Expression and RNA)	X												
Biomarker Collection (sE-selectin by ELISA)	X ^C	X ^{C,D}				X ^E					X ^F		X ^G

^A Cladribine at the assigned dose level IV over approximately 1 to 2 hours, daily on days 1-5 combined with cytarabine at the assigned dose level SQ twice daily on days 1-10. The cytarabine should be administered approximately 3-6 hours following the start of the cladribine infusion.

^B Uproleselan 800 mg IV on D1 and then IV Q12 hours on D2-12

^C Pre-dose samples prior to Day 1 dosing; 2 sample collections - Screening and Baseline prior to dosing

^D Day 1 sample – after uproleselan but prior to CLAD/cytarabine administration

^E Day 5 sample after CLAD regimen administration

^F Day 10 sample after cytarabine administration

^G Day 12 after final uproleselan administration; 1 hour post last dose

E-selectin mediated interactions may play a role in AML and the expression of E-selectin or its binding epitope (sialyl Lea/x) may predict the clinical course and patient outcomes in AML. Increased expression of E-selectin, as seen in inflammatory conditions, malignant states such as leukemia, and during

chemotherapy, is also associated with increased shedding of E-selectin from the cell surface resulting in higher levels of sE-selectin in the circulation.

We will measure the levels of E-selectin ligand on pretreatment bone marrow blasts in patients treated with uproleselan to describe the cell-surface expression pattern of E-selectin ligand on AML blasts and to determine the effect on clinical outcomes. We will also examine plasma sE-selectin at baseline and after treatment with chemotherapy and uproleselan to determine if E-selectin inhibition affects sE-selectin levels and to correlate plasma levels with clinical outcomes.

We will measure the expression of E-selectin ligand-forming glycosylation genes from pretreatment bone marrow blasts treated with or without uproleselan to describe the RNA expression levels of these genes on AML blasts and to determine the effect on clinical outcomes.

E-selectin is a cell adhesion glycoprotein that is expressed on endothelial cells and has been implicated in therapeutic resistance. In most myeloid leukemias, leukemic blasts express E-selectin ligands, which contain the glycan epitope of the carbohydrate sialyl Le^x (sLe^x). This sequestration in the bone marrow vascular niche, leading to cell adhesion-mediated drug resistance and resultant poor clinical outcome. Uproleselan is an E-selectin antagonist which interrupts leukemic cell homing to the vascular niche, increases susceptibility to cytotoxic and targeted therapies and can be a potent adjunct to therapeutics. In deed data has demonstrated a correlation between leukemic cell surface levels of E-selectin ligands using multiparameter flow cytometry and response to uproleselan.

Recently, transcriptome profiling of E-selectin ligand-forming glycosylation genes have been explored from public data sets to identify elevated E-selectin ligand expression in patients with AML. RNA-seq data from patients treated in COG AAML1031 ($N = 1,074$) was available for evaluation. Of 24 genes examined, Fucosyltransferase 7 (FUT7) and ST3 beta-galactoside alpha-2,3-sialyltransferase 4 (ST3GAL4) were significantly associated with adverse outcome ($HR = 1.013, p < 0.0001$, and $HR = 1.023, p < 0.0001$, respectively) and directly synthesize sLe^x. Patients highly expressing FUT7 (highest quartile of expression) had significantly worse outcome than lower expressors (lowest 3 quartiles of expression), with a 5-year OS of 50.3% vs. 68.3% ($p < 0.0001$). Similarly, those with high ST3GAL4 expression had a 5-year OS of 51.3%, compared to 68.1% for low expressors ($p < 0.0001$). High expression of these genes was shown to be associated with cell surface E-selectin ligand expression. Taken together these data suggest a strong correlation between transcriptome measurements of E-selectin ligand-forming glycosylation genes and cell surface glycosylation levels of E-selectin ligands, and lend support for the use of E-selectin ligand glycosylation genes as predictive biomarkers.

5.4.1 Soluble E-selectin Sampling and Processing

Care should be taken that blood for sE-selectin assessment is drawn from a vein apart from the site of investigational drug infusion (e.g., from a different limb or central line).

Blood (3-5 mL) will be drawn into sodium citrate tubes, inverted 3-4 times and stored in an ice bath until centrifugation. Samples will be centrifuged at 2000-2500 rpm at 4°C for 10 minutes. Ideally, samples should be immediately centrifuged following collection. If institutional staffing and/or logistics do not allow for this, samples may be stored (via an ice bath or at approximately 4°C) for 48-72 hours before centrifugation.

After centrifugation, pipette half of plasma into an appropriately labelled cryovial (primary aliquot). Pipette the remaining plasma into an additional appropriately labelled cryovials (back-up aliquot).

The aliquots will be stored in a freezer set at -70 to -80°C until shipped for analysis.

5.4.3 E-selectin ligand/RNA Sampling and Processing

1. Perform bone marrow procedure, as per institutional procedure
2. Collect 2 ml bone marrow aspirate in a Sodium Heparin tube
3. Immediately after sample is drawn, gently invert the tube 180° and back, 8-10 times.
 - a. Keep sample at AMBIENT TEMPERATURE

No additional specimen will be required for RNA testing. The sample collected for E-selectin ligand testing will provide sufficient material for RNA aliquoting.

5.5 Outside Physician Participation During Treatment

Interim visits can be provided by physicians outside MDACC. Additionally, in the event the patient cannot travel to MDACC for a new cycle visit, a telemedicine visit including laboratory review is acceptable and medications will be shipped directly to the patient. Local care for the patient includes routine blood work monitoring in between treatment cycles.

1. A letter to the local physician outlining the patient's participation in a clinical trial will request local physician agreement to participate in the patient's care.
2. Protocol required evaluations outside MDACC will be obtained by 'Care Everywhere' in EMR, fax, or email. Records obtained via fax or email will be and scanned into the patient's record.
3. Changes in drug dose and/or schedule must be discussed with and approved by the MDACC physician investigator or their representative prior to initiation and documented in the patient record.
4. MDACC investigators will perform all decisions regarding dose adjustments and treatment interruptions or re-initiation of treatment, grading and attribution of adverse events, and assessment of efficacy. The home physician will not make any decisions regarding dose adjustments and/or treatment interruptions or resumption of treatment, grading and/or attribution of adverse events, or assessing efficacy. These will all be done by the MDACC investigators.
5. Routine, standard-of-care laboratory assessments (and physical exam when/if needed) will be performed by the home physician.
6. A copy of the informed consent and treatment schema will be provided to the local physician.
7. Documentation to be provided by the local physician will include drug administration records, vital signs, ECOG, concomitant medications, and progress notes, reports of the protocol required laboratory and diagnostic studies, and documentation of any hospitalizations.
8. The home physician will be requested to report to the MDACC physician investigator all life-threatening events within 24 hours of documented occurrence.

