4.0 TREATMENT PLAN

This is a single arm phase Ib/II study in which patients will be treated with uproleselan given intravenously, combined with cladribine, (2-CDA, given intravenously [IV]) in combination low dose cytarabine (LDAC, given subcutaneously [SQ]) as induction therapy, followed by up to 6 cycles of consolidation/maintenance therapy composed of 2-CDA + LDAC (according to schema below) also in combination with uproleselan. In patients who do not achieve CR/CRi/MLFS after cycle 1, an additional course of re-induction with 2-CDA+LDAC+uproleselan may be given.

Treatment will be continued during the duration of the study unless patient exhibits evidence of clinically significant treatment failure, clinically significant disease progression, unacceptable toxicity, or if the investigator determines that discontinuation is in the best interest of the patient. Patients who do not achieve at least MLFS after two cycles of therapy will be taken off study. Relapsing patients may remain on the study if participation in the study is still providing disease control or clinical benefit and is considered in the best interest of the patient after discussion with the principal investigator.

Patients will be treated with the study drugs per protocol, based on the calculation of the patient's body surface area (BSA). The BSA will be calculated before each cycle and will be based on the patient's height and weight.

Patients will be instructed to self-administer cytarabine at home unless hospitalized and return unused drug in accordance with institutional guidelines. All induction and consolidation intravenous infusions will be administered at MD Anderson Cancer Center (MDACC) or at the MDACC Houston Area Locations (HALs).

The primary objective is to determine the safety of this combination and also to determine efficacy in achieving CR, CRi; and prolonging RFS and OS. All patients will be registered for the protocol via the Clinical Oncology Research (CORE) system at MDACC (single institution study).

The study will have 2 dose levels during lead-in, followed by an expansion cohort of 25 patients at the safe and tolerable dose level. All patients will be treated with the RP2D of uproleselan of 800 mg IV on D1 and then IV q12 hours on D2-12.

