 - i. Hematologic laboratory abnormalities will not be recorded as baseline events for patients with acute leukemia, myelodysplastic syndrome, chronic lymphocytic leukemia, or chronic myeloid leukemia in blast phase.
 - ii. If exact start date is unknown, month and year or year may be used as the start date of the baseline event.
2. The maximum grade of the adverse event will be captured per course or protocol defined visit date.
3. These adverse events will be recorded in the case report form:
 - a. Any grade adverse event that is possibly, probably, or definitely related to the study drug(s).
 - b. All serious adverse events regardless of attribution to the study drug(s).
 - c. Any grade adverse event regardless of attribution to the study drug(s) that results in any dose modification.
4. Hematologic adverse events will not be recorded or reported for studies in patients with acute leukemia, myelodysplastic syndrome, chronic lymphocytic leukemia, or chronic myeloid leukemia in blast phase except for:
 - a. Prolonged myelosuppression as defined by the NCI-CTCAE criteria specific for leukemia, e.g. marrow hypocellularity on day 42 or later (6 weeks) from start of therapy without evidence of leukemia (< 5% blasts), or that results in dose modifications, interruptions or meets the protocol definition of DLT or SAE.
5. Serious adverse events will be reported according to institutional policy.
6. Protocol specific language regarding the recording and reporting of adverse and serious adverse events will be followed in the event of discordance between the protocol and Leukemia-specific adverse event recording and reporting guidelines.

The investigator (or physician designee) is responsible for verifying and providing source documentation for all adverse events and assigning the attribution for all adverse events for subjects enrolled.

Serious Adverse Event (SAE) Reporting Requirements

An adverse event or suspected adverse reaction is considered “serious” if, in the view of either the investigator or the sponsor, it results in any of the following outcomes:

- Death
- A life-threatening adverse event
- Inpatient hospitalization or prolongation of existing hospitalization.
- A persistent or significant incapacity or substantial disruption of the ability to conduct normal life functions.
- A congenital anomaly/birth defect.

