Important medical events that may not result in death, be life-threatening, or require hospitalization may be considered a serious adverse drug experience when, based upon appropriate medical judgment, they may jeopardize the patient or subject and may require medical or surgical intervention to prevent one of the outcomes listed in this definition. Examples of such medical events include allergic bronchospasm requiring intensive treatment in an emergency room or at home, blood dyscrasias or convulsions that do not result in inpatient hospitalization, or the development of drug dependency or drug abuse (21 CFR 312.32).

Important medical events as defined above may also be considered serious adverse events. Any important medical event can and should be reported as an SAE if deemed appropriate by the Principal Investigator or the IND Sponsor.

- All events occurring during the conduct of a protocol and meeting the definition of a SAE must be reported to the applicable Institutional Review Board (IRB) of record in accordance with their timeframes and procedures.
- Serious adverse events will be captured from the time of consent until 30 days after the last dose of drug or protocol specific timeline, unless the participant withdraws consent.
- Serious adverse events must be followed until clinical recovery is complete and laboratory tests have returned to baseline, progression of the event has stabilized, or there has been acceptable resolution of the event.
- All SAEs, including the development of new malignancies, must be reported to the IND/IDE Sponsor **within 24 hours of knowledge of the event** regardless of the attribution.
- Additionally, any serious adverse events that occur after the 30-day time period that are related to the study treatment must be reported to the IND/IDE Sponsor. This may include the development of new malignancies.
- All events reported to the supporting company must also be reported to the IND/IDE Sponsor.

Reporting to FDA:

Serious adverse events will be reported to the FDA by the IND/IDE Sponsor according to 21 CFR 312.32. For SAEs determined by the IND Sponsor to meet the criteria for prompt reporting to the FDA, the principal investigator will be provided with a MedWatch form. The completed MedWatch form must be returned to the IND Sponsor by the due date specified by the IND Sponsor.

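### Section 5.5 asks home physicians for 24-hour notice of life-threatening events only, so a locally managed death, admission or other SAE can reach the investigators late

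*Combined protocol and SAP*

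**What the plan says.** Section 5.5 opens local care broadly and excludes no cycle: "Interim visits can be provided by physicians outside MDACC". Item 8 then sets the one timed duty: "The home physician will be requested to report to the MDACC physician investigator all life-threatening events within 24 hours of documented occurrence". Item 7 lists the records the local physician supplies, including progress notes "and documentation of any hospitalizations", with no date by which they are due. Item 4 keeps judgement at the trial site: "MDACC investigators will perform all decisions regarding dose adjustments and treatment interruptions or re-initiation of treatment, grading and attribution of adverse events".

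Section 10.2 defines serious events more widely. Besides life-threatening events it lists death, "Inpatient hospitalization or prolongation of existing hospitalization", lasting incapacity and birth defect, and then adds important medical events. On reporting it states: "All SAEs, including the development of new malignancies, must be reported to the IND/IDE Sponsor". The limit is 24 hours, counted from knowledge of the event, whatever the attribution.

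Section 5.5 also covers a patient who cannot travel for a new cycle: "a telemedicine visit including laboratory review is acceptable and medications will be shipped directly to the patient". Section 4.0 says "All induction and consolidation intravenous infusions will be administered at MD Anderson Cancer Center (MDACC") or at its Houston-area locations, and has BSA recalculated before each cycle. Section 5.2a puts examination, vital signs, weight and performance status before each cycle.

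**The concern.** The protocol's own list of serious outcomes is wider than the list it asks local physicians to act on. A patient who dies in a local hospital, or is admitted there for a non-life-threatening toxicity, meets section 10.2, yet no timed request covers the event. Because grading, attribution and dosing decisions belong to the site, that assessment waits until the site hears. Between visits patients may be giving themselves cytarabine at home (section 4.0), so the delay can matter for the individual as well as for the safety record.

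Item 8 also asks the home physician to sort events by severity before deciding whether to call, which sits awkwardly with item 4.

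For the statistics, the question is whether a DLT managed locally could be unknown when a cohort is reviewed.

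**Working it through.** **1. Coverage of the timed request.** Section 10.2 gives five listed outcomes (death, life-threatening, hospitalisation, incapacity, birth defect) plus important medical events: 5 + 1 = 6 categories. Item 8 times one of them. Hospitalisations are documented under item 7 without a deadline. For the rest, including death, section 5.5 gives no time.

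**2. The sponsor clock.** Section 10.2 counts 24 hours from knowledge and does not say whose. If it means the investigator's, a late local report moves the start of the clock; it does not overrun it.

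**3. Which events feed the counts.** DLTs are cycle 1 events (sections 4.1.3 and 8.0), and the phase II toxicity rule also uses cycle 1. Section 5.0 says patients usually spend the first month in hospital under daily observation, and the cycle 1 schedule has three examinations a week. The phase II cohort summary waits until patients finish cycle 2; the phase Ib summary follows cycle 1 directly. What stays exposed is a patient discharged early or followed locally late in cycle 1. One example is the DLT of grade 4 cytopenia beyond day 42, which falls after the usual inpatient month.

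**4. Phase Ib illustration.** Section 8.0 escalates at an observed rate of 0.236 or less, de-escalates at 0.359 or more, and requires a rate below 30% for the RP2D.
- 0/3 = 0 means escalate; 1/3 = 0.333 means stay.
- 1/6 = 0.167 meets the RP2D condition; 2/6 = 0.333 fails it.

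One DLT unknown at the review would change either decision. The documents give no frequency for this.

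**5. Phase II stopping rule.** Plan figures first. Toxicity boundary: the smallest x with Pr(p > 0.30) > 0.95 under Beta(0.6 + x, 1.4 + n − x). This gives 4/5, 6/10, 8/15 and 10/20, as in Table 8. Futility boundary: the largest x with Pr(p < 0.45) > 0.99 under Beta(1 + x, 1 + n − x). This gives none, 0/10, 2/15 and 3/20, also as in Table 8. The historical rates are taken as fixed; tight beta priors give the same boundaries. Early stopping is 1 − (probability of passing all toxicity looks) × (probability of passing all futility looks), with the two outcomes independent. All 16 entries of Table 9 reproduce within 0.005. At an ORR of 0.45 and toxicity 0.20, 0.30, 0.40, 0.50, the calculation gives 0.027, 0.111, 0.344, 0.668 against 0.03, 0.11, 0.34, 0.67.

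Now suppose a share m of the newest cohort's DLTs is unknown at each look and all older ones are known. The value of m is an assumption; the documents give none. Probability of stopping on toxicity alone:

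| True toxicity | m = 0 | 5% | 10% | 20% | 30% |
|---|---|---|---|---|---|
| 0.30 | 0.099 | 0.091 | 0.083 | 0.068 | 0.055 |
| 0.40 | 0.335 | 0.317 | 0.299 | 0.262 | 0.227 |
| 0.50 | 0.664 | 0.643 | 0.621 | 0.576 | 0.528 |

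If the missed DLTs were never counted at all (an upper bound, not late reporting), stopping at toxicity 0.50 would be 0.499 with 10% missed and 0.335 with 20%. Step 3 gives reason to expect small m in phase II.

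**6. Telemedicine sentence.** Every cycle contains IV cladribine and IV uproleselan (Table 2), and section 4.0 fixes where infusions are given. Section 5.5 speaks of shipped medications without naming them. Items 5 and 7 provide for a local examination when needed, vital signs and ECOG status, but do not list weight, which sections 4.0 and 5.2a use before each cycle.

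**The case against.** The strongest reply is that the system already catches these events. Item 7 obtains hospitalisation records, item 2 gives routes for outside records to arrive, and item 3 requires any change of dose or schedule to be cleared with the site beforehand. Cycle 1, the only cycle that counts for DLTs, is mostly inpatient. Many local admissions would not be DLTs anyway: section 4.1.3 leaves out most infections and readmissions with grade 3 toxicity, and counts hospitalised grade 3 nausea, vomiting or diarrhoea only when no other cause is definite. All of this stands, and it keeps the statistical effect small. It does not supply the missing deadline.

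Three stronger readings are tempting and not supported.
- A reader might infer that the 24-hour SAE limit will be missed. It runs from knowledge, so the supportable claim is delayed awareness.
- A reader might infer that the stopping rules are compromised. The cycle 1 window, inpatient care and the wait for cycle 2 in phase II argue against that.
- A reader might infer that a site must break section 4.0 to follow the shipping sentence. Shipped medications can mean self-administered cytarabine, with infusions still given at the centre or its Houston-area locations. The text is ambiguous rather than shown to be contradictory.

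**Conclusion.** The point holds as a gap in prompt notification. One of six serious categories carries a timed local request, and the others can reach the only people allowed to grade, attribute and decide on dosing after an unspecified delay. No stated SAE deadline is breached, on the assumption that the knowledge in section 10.2 is the investigator's.

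The statistical consequence is small. It lies mainly in phase Ib, for patients seen locally late in cycle 1, where a single late-known DLT could change a cohort decision. In phase II, even an assumed 10% to 20% of the newest cohort's DLTs being unknown would lower stopping at a true toxicity of 0.50 from 0.664 to between 0.621 and 0.576, and the timing of the summaries makes such shares unlikely. The dose-finding rules and Tables 6 to 9 need no change on this account. The shipping sentence is a secondary matter of clarity.

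**What to change.** 1. Reword item 8, and the letter that item 1 describes, so that the home physician is asked to notify the site, within 24 hours of becoming aware, of any event meeting the section 10.2 SAE definition, naming death and any hospitalisation explicitly. Do not tie the request to a toxicity grade, since item 4 leaves grading with the site.
2. Before each cohort summary, have the site confirm with any home physician involved that cycle 1 events and blood counts are complete. This step is needed for the late cytopenia DLT, which need not be an SAE and so might not be caught by the first change.
3. Reconcile the telemedicine and shipping sentence with sections 4.0 and 5.2a: state which drug or drugs it refers to, and how weight, BSA, vital signs, performance status and examination are obtained for that cycle.

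The cost is a short protocol amendment, a revised letter, and somewhat more reporting work for local physicians, including some calls about admissions that prove unrelated. No sample size, boundary or operating characteristic changes.
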